This application is an investigator-initiated, University-sponsored academic research program. Sinapi Biomedical are sub-contracted to supply the device. Sinapi manufactures a CE marked Ellavi balloon uterine tamponade system (Fig 1). The central tube is very similar to the Levin tube, but without the multiple suction holes, and served as the starting point for development of the U-STAT device.

Methods

This exploratory proof of concept (POC) clinical trial will build on our experience with our initial clinical studies of the improvised STUT device. This initial trial is designed to assess essential safety, performance, feasibility and acceptability and to give an indication of effectiveness and suitability for a substantive randomized effectiveness trial. It will include a limited number of participants (intervention arm n=40, control arm n=40).

Study type: Investigator-initiated, academic, non-commercial study.

Study Sponsor. Wits Health Consortium, a subsidiary of University of the

Witwatersrand

Study Design: Prospective intervention study

Study Sites: Frere/Cecilia Makiwane hospitals, South Africa

Study Duration: Four months

Study Population: Women 18 years old or more with risk factor(s) for PPH, for planned vaginal or caesarean birth; no serious medical conditions.

Inclusion Criteria

- Age 18 years and older
- Planned vaginal or caesarean birth
- One or more risk factors for PPH. These include
 - o Previous PPH
 - o Hypertension and pre-eclampsia
 - o Induction of labour
 - o Emergency caesarean birth
 - O Anaemia
 - Multiple pregnancy
 - Polyhdramnios
 - Macrosomia
 - Antepartum haemorrhage
- No serious medical conditions
- Provision of signed written informed consent

Intervention: Suction Tube Uterine Tamponade (STUT) using the purpose-designed soft plastic suction catheter inserted after vaginal birth or during caesarean birth. Low-pressure suction applied (approx. 100mmHg). Suction stopped after 30 minutes. If no further bleeding, tube removed. If bleeding resumes, suction continued. If bleeding not controlled within 20 min (or sooner if clinically indicated), proceed to further management according to local standard of care protocols (these might include additional uterotonics, tranexamic acid, compression methods, uterine balloon tamponade or laparotomy).

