Control: This is a pilot proof of concept study with sample size insufficient for a formal randomized comparison. In order to have a valid comparator, participants will be randomly allocated to an intervention and control group (approx. 40 per group). No p values will be calculated. Comparisons will be as risk ratios or mean differences with 95% confidence intervals.

Outcomes

Baseline demography and clinical data will be recorded.

Primary: The primary outcome is the combined frequency of adverse device effects and device deficiencies up to discharge from hospital.

Adverse device effects (ADEs) encompass any adverse event with a reasonable causal relationship resulting from insufficient or inadequate instructions for use; problems with the deployment, implantation, installation, or operation of the device; malfunction of the device; or user error or intentional misuse of the device. They will include device deficiencies such as device expulsion / falling out of the uterus, failed maintenance of suction pressure and tube blockage.

A Serious Adverse Device Effect (SADE) is an adverse device effect that has resulted in any of the consequences characteristic of a serious adverse event. An example of this would be the need for further intervention to treat trauma caused by the device (e.g. sutures, laparotomy, etc).

Secondary efficacy outcomes will include:

- 1. Measured blood loss within 30 minutes after insertion (ml)
- 2. Blood loss >500ml
- 3. Blood loss >1000ml
- 4. Efficiency of suction (assessed through ultrasound assessment of residual blood in the uterus at 30 minutes or blood expressed from the uterus after tube removal)
- 5. Blood pressure, pulse and shock index 15 minutes after vaginal birth or caesarean
- 6. Change in routinely collected haemoglobin levels pre delivery to post delivery
- 7. Blood transfusion
- 8. ICU admission
- 9. Death
- 10. Functionality and acceptability:
 - a. Active bleeding from the uterus continuing for more than 10 minutes (main efficacy outcome).
 - b. Any adverse event
 - c. Pain experienced (No pain/Mild /Severe/Unbearable)
 - d. Need for Additional interventions to stop bleeding (e.g. more uterotonics, compressive measures, UBT, laparotomy, hysterectomy)
 - e. Was STUT effectively inserted? (Yes/No/Unknown)
 - f. How easy was it for health care providers to insert the Suction Tube Uterine Tamponade (easy/moderately difficult/Difficult/failed)

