Enrolment will take place immediately after birth of the baby when the participant's name is entered in the enrolment register and allocation takes place by opening the next in a consecutively numbered series of opaque sealed envelopes with allocation cards in computer-generated random sequence in balanced blocks of variable size, stratified by mode of birth. Participants will remain in the trial whether or not the intervention is applied, on the 'intention to treat' principle. Good Clinical Practice (GCP) procedures will be followed.

A clinical checklist will be completed by the attending clinician, which will form part of the patient clinical record. Data will be entered onto paper or electronic CRFs by the research staff.

Quality control will be performed on-site: the research staff will be responsible for ensuring that the CRFs are correctly filled out. Completed CRFs will be checked against the original patient records for correct completion. Any discrepancies will be immediately addressed.

Data management

Because of the small number of participants and limited data per participant, complex data entry strategies will not be needed. Data will be entered onto paper or electronic CRF's, checked for accuracy at source, and stored in a locked filing cabinet or password-protected computer. The data will be entered onto an excel spreadsheet and analysed using Epi Info software.

Adverse events and serious adverse events, whether thought to be related to the trial intervention or not, will be recorded by the site PIs on standard adverse events forms which will be submitted to the University ethics committee and DSMC.

Data protection procedures

The following measures will be taken to ensure participant confidentiality:

- Trial data sets for each participant will be identified by a unique ID number, not the participant's name
- The trial register of names and trial ID numbers, and consent forms will be kept separate from the CRFs
- Trial documents will be kept securely under lock and key and will not be accessible, other than to the research teams
- Data will be entered by trial ID number onto a password-protected database to which only trial staff will have access
- The trial report will not contain the names of any participants
- After completion of the trial, the trial documents will be kept under lock and key for five years

Personal information

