The clinical trial will include use of personal demographic and clinical information of participants. The information will be de-identified using a trial ID number and stored in a password-protected computer. Paper trial documents will be stored under lock and key.

Data analysis

Data management will be conducted by the Liverpool University Clinical Trials Unit. The locked database will then be passed to the investigators for analysis.

For continuous variables, the number of participants, number of missing values, minima, maxima, means and standard deviations will be reported, with 95% confidence intervals. If distribution is not normal, medians and interquartile range (IQR) will be reported.

For categorical variables, the number of participants, number of missing values and percentages will be reported, with 95% confidence intervals.

Comparisons will be expressed as risk ratios or mean differences with 95% confidence intervals. As the study is not powered for statistical analysis, no p values will be reported.

Data sharing and access

Data will be made available after publication of results on reasonable request based on an ethically approved research protocol. Data sharing is included in the participant information.

Trial registration

The protocol will be registered with SANCTR and ISRCTN.

Research team

[name] is a senior researcher with expertise in clinical trials. **[name]** is a researcher with many years' experience conducting non-regulatory and regulatory clinical trials

The Trial Management Group will be responsible for governance and oversight. [name] will be overall responsible for the clinical trial conduct, whilst [name] will supervise the clinical trial.

Facilities

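### Allocation is stratified by mode of birth, but the stated between-arm comparisons do not carry the stratum; a plain two-arm analysis would give unbiased but somewhat too wide intervals for the secondary outcomes

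*Protocol*

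**What the plan says.** - **Allocation** (Quality assurance, During recruitment): a "computer-generated random sequence in balanced blocks of variable size, stratified by mode of birth". The ratio is 1:1, with 40 per arm.
- **Comparison** (Methods, Control): "No p values will be calculated. Comparisons will be as risk ratios or mean differences with 95% confidence intervals".
- **Comparison again** (Data analysis): "Comparisons will be expressed as risk ratios or mean differences with 95% confidence intervals", followed by "As the study is not powered for statistical analysis, no p values will be reported".
- **Mix of modes** (Sample size): at least a quarter of the device group must be vaginal births and at least a quarter caesarean. The caesarean share can therefore lie anywhere from 25% to 75%.
- **Analysis plan** (Before recruitment): a draft exists and is to be completed before the first participant is recruited. It is not shown.

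Neither statement of the comparison names mode of birth, and neither says whether the estimates are unadjusted or stratified.

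**The concern.** Stratified blocks keep the two modes nearly balanced between arms, so differences between modes largely drop out of the arm contrast. An ordinary two-sample standard error does not use this and still counts the between-mode spread as noise. The interval is then wider than the design requires and covers more than 95%.

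Mode of birth is a plausible source of such spread here, because the protocol also collects outcomes differently by mode:

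- **Blood loss.** The vaginal checklist measures tray and suction-bottle volumes. The caesarean checklist adds an estimate of surgical loss.
- **Vital signs.** The outcome is "Blood pressure, pulse and shock index 15 minutes after vaginal birth or caesarean". In the vaginal checklist the 15 minutes run from device insertion. In the caesarean checklist they run from placental delivery, and the item stands before the one for skin closure.

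The trial is meant to give an indication of effectiveness and to inform a larger trial. With 40 per arm and no p values, the interval is the whole comparative result, so precision matters.

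**Working it through.** **Inputs**

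- From the protocol: 40 per arm; caesarean share q between 0.25 and 0.75; caesarean blood loss mean 558 mL, SD 496 mL (Background).
- Assumed: everything about blood loss at vaginal birth, for which the protocol gives no figure, and all event rates by mode. The protocol states no precision for the comparisons, so there is no planned figure to reproduce.

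**Step 1. Mean blood loss: formula.** Let W be the average within-mode variance and D the difference in means between modes. With modes balanced across arms:

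- stratified width = 2 × 1.96 × √W × √(2/40)
- plain two-arm width = 2 × 1.96 × √(W + q(1−q)D²) × √(2/40)
- excess = √(1 + q(1−q)D²/W) − 1

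**Step 2. Within-mode SD of 496 mL in both modes, q = 0.5.** The stratified width is 435 mL.

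| D (mL, assumed) | Plain width (mL) | Excess |
|---|---|---|
| 100 | 437 | 0.5% |
| 200 | 444 | 2.0% |
| 300 | 454 | 4.5% |
| 500 | 487 | 12.0% |

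At q = 0.25 or 0.75 the excess is smaller (3.4% at D = 300).

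**Step 3. Separate SDs by mode.** The caesarean mean and SD stay at 558 and 496 mL. W = q × 496² + (1−q) × (vaginal SD)², and D = 558 − vaginal mean.

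| Vaginal mean / SD (assumed) | D | q | W | q(1−q)D² | Excess |
|---|---|---|---|---|---|
| 400 / 350 | 158 | 0.75 | 215,137 | 4,681 | 1.1% |
| 300 / 250 | 258 | 0.50 | 154,258 | 16,641 | 5.3% |
| 200 / 150 | 358 | 0.25 | 78,379 | 24,031 | 14.3% |

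Simulated log-normal losses gave the same picture. Plain 95% intervals covered about 95.5-98%. Across the scenarios the ratio of stratified to plain width ran from 0.989 to 0.865, so the plain interval was 1/0.989 − 1 = 1.1% to 1/0.865 − 1 = 15.6% wider. The top of this range is the corner with a vaginal mean of 200 mL and 75% vaginal births.

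A larger excess is possible on paper: a common SD of 300 mL with D = 500 gives 30%. But against the caesarean mean of 558 mL, D = 500 implies a vaginal mean of 58 mL, and 300 mL is well below the only SD the protocol quotes. I set that case aside.

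**Step 4. Binary outcomes.** With exact balance and a true risk ratio of 1, the ratio of plain to stratified standard error is √[p̄(1−p̄) / Σ w p(1−p)]. Here p is the risk in each mode, w the mode's share and p̄ the overall risk. With equal shares:

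| Risk, vaginal / caesarean (assumed) | p̄(1−p̄) | Σ w p(1−p) | Excess |
|---|---|---|---|
| 10% / 10% | 0.0900 | 0.0900 | 0% |
| 2% / 10% | 0.0564 | 0.0548 | 1.5% |
| 10% / 30% | 0.1600 | 0.1500 | 3.3% |
| 14% / 41% | 0.1994 | 0.1812 | 4.9% |
| 10% / 50% | 0.2100 | 0.1700 | 11% |

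Simulated log risk ratios with Mantel-Haenszel standard errors agreed: median ratios of 1.00 at 10/10%, 1.01 at 2/10%, 1.03 at 10/30% and about 1.11 at 10/50%. With exact 1:1 balance within modes, the plain and Mantel-Haenszel risk ratios are the same number. Only the interval changes.

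**The case against.** The strongest objection is that the protocol never says the comparisons are unadjusted. A Mantel-Haenszel risk ratio is a risk ratio, and a mode-adjusted mean difference is a mean difference, so the present wording permits either analysis. The choice of estimator is often left to an analysis plan, and one exists here that is not shown. This stands. A reader might infer that the protocol prescribes crude intervals, and the text does not support that. What remains is that the protocol states the comparison twice, together with its effect measures and interval, and both times leaves out the factor it stratified on.

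A reader might also infer that the plan wastes up to a quarter of the sample (0.865² ≈ 0.75). That figure comes from one corner of an assumed grid. The protocol gives no vaginal blood-loss figure from which to derive it, and with less extreme assumptions the excess is a few percent.

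Three further points stand:

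- The primary outcome needs a device and is in substance not a between-arm comparison. It is untouched, as is the sample size built on it.
- Outcomes likely to be uncommon, such as ICU admission or death, gain almost nothing. No gain can be shown for the main efficacy outcome, bleeding beyond 10 minutes, because no rates by mode are given.
- The consequence is mild. The protocol itself says "This is a pilot proof of concept study with sample size insufficient for a formal randomized comparison", and no decision rule depends on interval width.

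Stratified estimates can also be fragile. At the 25% minimum the smaller stratum has about 10 per arm, so rare outcomes may have no events there.

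**Conclusion.** The point holds in a limited form. Allocation is stratified by mode of birth and the stated comparisons do not carry that stratum. If they are run as plain two-arm comparisons, the estimates are unbiased and the intervals conservative. For mean blood loss the excess width is typically a few percent, reaching about 14-16% only under an extreme assumed difference between modes. For uncommon binary outcomes it is about 0-3%, and it approaches or passes 10% only where risks differ strongly by mode. If the modes do not differ, there is no excess.

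The direction is certain. The size rests on assumed vaginal-birth figures and event rates. Severity is modest: precision is lost on secondary outcomes, with no threat to validity.

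**What to change.** Add one sentence to the Control paragraph and to the Data analysis section, for example: *Between-arm comparisons of secondary outcomes will be stratified by or adjusted for mode of birth (Mantel-Haenszel risk ratio where events allow; mean difference from a linear model with a mode-of-birth term), and results will also be described by mode.* The analysis plan should say the same, and should name what is reported when events are too few to stratify. The results by mode should be descriptive only, given the small strata.

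The cost is a sentence in each place. Mode of delivery is already item 10 of the clinical record form, so no new data and no more participants are needed.

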19. Tamponade device inserted? 2=Other tube*; 3=Ellavi; 4 = Other	· ·				
20. Time device inserted:		:			

21. Ease of insertion? 1=easy, 2=mod.diff, 3=difficult		
22. Device stable in uterus? 0=No; 1=Yes		
23. Tube air leak? 0=No; 1=Yes; 3=No tube		
25. Effect of device on exam/mx? 1. Facilitated, 2. Interfered, 3.Neither		
26. Exam obscured by blood from ut: 0=No; 1=Yes		
27. Time bleeding stopped.	:	
28. Time vital signs check (+ 15min)	:	
29. Syst BP mmHg		
30. Diast BP mmHg		
31. Pulse /m		
32. Additional oxytocin 0 = No 1= Yes		
33. Additional erg-/syntomentrine 0 = No 1= Yes		
34. Additional misoprostol 0 = No 1= Yes		
35. Additional tranexamic acid 0 = No 1= Yes		
36. Time blood collection measured (>30 min)	:	
37. Blood volume excluding suction jar (ml)		
38. Blood volume in suction jar (ml)		
39. Blood expelled ex ut. after removal of device or after 30 min in control group (ml)		
40. If bleeding persists, measured blood loss post 30min		
41. Laparotomy 0 = No 1= Yes		
42. Compression sutures 0 = No 1= Yes		
43. Uterine devascularization 0 = No 1= Yes		
44. Hysterectomy 0 = No 1= Yes		
45. Other procedure 0 = No 1= Yes*		
46.ICU admission 0 = No 1= Yes		
47. Organ failure 0 = No 1= Yes*		

48. Death 0 = No 1= Yes		
49. Blood transfusion (number of units RBCs)		
50. First Haemoglobin after bleeding controlled (g/dL)		
51. Highest temperature (deg C)		
52. Endometritis 0 = No 1= Yes 9=Unknown		
53. Other complications 0 = No 1= Yes* 9=Unknown		
53. Date of Discharge (DD/MMM/YY)	/ /	

Completed by (initials) :	Date completed	(dd/mmm/yy)
Completed by (initials) .	Date completed	(dd/IIIIIII/yy

Vaginal birth Clinical checklist (remains in hospital records)

Equity for Suction Tamponade Access to treat postpartum haemorrhage: The ESTA project

	1.	○ Consent signed
	2.	Confirm with Mother that still happy with consent
	3.	Ostudy trolley is available with register, U-STAT suction tubes, working suction
	4.	Clean drape or Maternawell tray available
	5.	\bigcirc Manual suction device ready with vacuum pumped or suction machine pressure set to 100mmHg – block tubing to check
	6.	After baby born position drape/Maternawell tray below the buttocks
Aft	er p	lacenta delivered completely:
	7.	Examine vaginally to exclude major lower genital tract trauma
	8.	O Note the time, 24 hr: H H : M M
	9.	○ Open next numbered envelope and note allocation: ○ STUT* ○ Control
	10.	*Insert U-STAT tube to fundus of uterus and start suction
	11.	\bigcirc *Insertion of tube; \bigcirc easy, \bigcirc moderately difficult, \bigcirc difficult, \bigcirc Failed, \bigcirc not done
	12.	Alternative Management
	13.	*Time tube insertion procedure completed 24 hr: H H : M M
	14.	*Check tube/balloon stable in uterus Yes / No / Onot used
	15.	Ocontinue routine care including repair of bleeding tears
	16.	*Effect of device on exam/mx of lower genital tract bleeding? Facilitated; Interfered; Neither; Unknown
	17.	○ Note the time per vaginal bleeding stopped. 24 hr: H H : M M
	18.	○ 15 minutes after insertion (10 above) note time 24 hr: H H : M M
		Systolic BP Diastolic Pulse
	19.	○ 30 minutes after insertion, note time. 24 hr: H H : M M
	20.	
		ml ml
	21.	Replace empty tray, expel blood from the uterus by fundal massage (into tray)
	22.	○ Measure blood loss in tray = RESIDUAL
		ml ml
	23.	*disconnect suction. If no bleeding in 10 minutes, remove U=STAT tube
	2/	*If bleeding continues replace empty tray continue suction plus other measure

25. When bleeding stopped, measure blood loss in tray = Secondary blood loss
ml ml
26. *Measure blood loss in suction bottle
ml ml
27.
○ None
The participants will be followed till discharge and the outcome data, as well as any complications, recorded.

Caesarean birth Clinical checklist (remains in hospital records)

Equity for Suction Tamponade Access to treat postpartum haemorrhage: The ESTA project

	1.	○ Consent signed
	2.	Oconfirm with Mother that still happy with consent
	3.	OStudy trolley is available with register, U-STAT suction tubes, working suction
	4.	Clean drape or Maternawell tray available for post-op use
	5.	○ Manual suction device ready with vacuum pumped or suction machine pressure set to 100mmHg – block tubing to check
	6.	\bigcirc After birth of baby, open next numbered envelope and note allocation: \bigcirc STUT* \bigcirc Control
Aft	er p	placenta delivered completely:
	7.	○ Note the time, 24 hr: H H : M M
	8.	\bigcirc *Insert U-STAT tube to fundus of uterus and lower end through cervix and vagina, ask assistant to connect and start suction
	9.	\bigcirc *Insertion of tube; \bigcirc easy, \bigcirc moderately difficult, \bigcirc difficult, \bigcirc Failed, \bigcirc not done
	10.	. Alternative Management
	11.	. *Time tube insertion procedure completed 24 hr: H H : M M
	12.	. Continue uterine closure
	13.	*Effect of device on visualisation for uterine closure? \(\text{Facilitated}; \text{Interfered}; \) Neither; \(\text{Unknown}\)
	14.	. Time uterus closed 24 hr: H H : M M
	15.	. Measure blood volume in suction bottle = pre-suction volume:
		ml ml
	16.	*Note the time bleeding through suction tube stopped. 24 hr: H H : M M
	17.	. O 15 minutes after placental delivery (7 above) note time 24 hr: H H : M M
		Systolic BP Diastolic Pulse
	18.	. After skin closure, estimate surgical blood loss (excluding U=STAT tube drainage)
		ml ml
	19.	. O In recovery room: Place drape or Maternawell tray under participant's buttocks
	20.	
	21.	. O 30 minutes after placental delivery (7 above), note time. 24 hr: H H : M M
	22.	. Swab vagina and measure blood loss in drape/tray = postop blood blood

23. O Place new tray or drape under participant and express blood from uterus -
Measure blood loss in drape/tray = RESIDUAL blood
ml ml
24. *Disconnect suction, if no bleeding after 10 minutes, remove U-STAT tube. If
bleeding resumes, reconnect suction and manage as per hospital protocol
25. *Measure blood loss in suction bottle
ml ml
26. *Suction tube problems: Fell out; blocked; leaking; Poor suction
○ None

ml

The participants will be followed till discharge and the outcome data, as well as any complications, recorded.

Participant questionnaire (Vaginal birth Intervention group only)

Protocol Title: Equity for Suction Tamponade Access to treat postpartum haemorrhage: The ESTA project			
Site Number:	Subject ID:	Date:(dd/mmm/yy)	
Dear Participant, thank you for assisting us with the ESTA project. Pease would you answer the following questions. There are no right or wrong answers. Please just give us your personal opinions. Please feel free not to answer if you prefer not to.			
Questionnaire		Comment/Notes	
*After the hirth of your ba	by a tubo was	T	
*After the birth of your baby, a tube was inserted to your uterus to help reduce bleeding Please could you describe the pain you experienced? 0=No pain; 1 = Mild pain; 2 = Severe pain; 3 = Unbearable pain; 4 = unsure; 9 = no data			
*Please could you describe when the tube was removed = Mild pain; 2 = Severe pain Unbearable pain; 4 = unsure	d? 0=No pain; 1 u; 3 =		
*Please could you describe overall about the suction tub 0= fine; 1 = uncomfortable b = Unacceptable; 3 = Unbear unsure; 9 = no data	pe procedure? out acceptable; 2		
Thank you for assisting with this questionnaire			

Date completed

(dd/mmm/yy)

Completed by (initials):

Participant questionnaire (Caesarean birth Intervention group only)

Protocol Title: Equity for Suction Tamponade Access to treat postpartum haemorrhage: The ESTA project			
Site Number:	Subject ID:		Date:(dd/mmm/yy)
Dear Participant, thank you for assisting us with the ESTA project. Pease would you answer the following questions. There are no right or wrong answers. Please just give us your personal opinions. Please feel free not to answer if you prefer not to.			
Questionnaire			Comment/Notes
D : 4			
During the caesarean operation, a tube was inserted to your uterus to help reduce bleeding. Please could you describe the pain you experienced from the tube? 0=No pain; 1 = Mild pain; 2 = Severe pain; 3 = Unbearable pain; 4 = unsure; 9 = no data			
Please could you describe how you felt when the tube was removed? 0=No pain; 1 = Mild pain; 2 = Severe pain; 3 = Unbearable pain; 4 = unsure; 9 = no data			
Please could you describe how you felt overall about the suction tube procedure? 0= fine; 1 = uncomfortable but acceptable; 2 = Unacceptable; 3 = Unbearable; 4 = unsure; 9 = no data			
Thank you for assisting with this questionnaire			

Completed by (initials):	Date completed	(dd/mmm/yy)
--------------------------	----------------	-------------

Health care provider questionnaire (Vaginal birth Intervention group only)

Protocol Title: Equity for Suchaemorrhage: The ESTA p	=	cces	s to treat postpartum
Site Number:	Subject ID:		Date:(dd/mmm/yy)
Dear Health care provider, thank you for assisting you answer the following questions. There are no give us your personal opinions. Please feel free			nt or wrong answers. Please just
Questionnaire			Comment/Notes
After birth of the baby and placenta, how easy was it to insert the suction tube in the uterus? 0=Easy; 1 = Difficult; 2 = Very difficult; 3 = not possible; 4 = unsure; 9 = no data			
Was the suction tube stable in the uterus? 0=No; 1 = Stable; 2 = fell out; 3 = not used; 4 = unsure; 9 = no data			
Did the suction tube leak air Leaked a little; 2 = leaked a = unsure; 9 = no data	•		
Did the suction tube get blockled and cleared; 2 = blockled removed; 3 = not used; 4 = data	ocked had to be		
Did the suction tube appear uterine contraction and redu 0=No; 1 = A little; 2 = A lot; 3 unsure; 9 = no data	icing blood loss?		
Was the suction tube easy t 1 = A little difficult; 2 = Very used; 4 = unsure; 9 = no da	difficult; 3 = not		
Please could you describe habout the suction tube procenegative; 1 = Positive; 2 = N; 9 = no data	edure? 0=		
Thank you for assisting with	this questionnaire		

Completed by (initials) :	Date completed	(dd/mmm/yy)
---------------------------	----------------	-------------

Health care provider questionnaire (Caesarean birth)

Protocol Title: Equity for Suction Tamponade Access to treat postpartum haemorrhage: The ESTA project				
Site Number:	Subject ID:		Date:(dd/mmm/yy)	
Dear Health care provider, the you answer the following que give us your personal opinion	estions. There a	re no rigi	ht or wrong answers. F	Please just
Questionnaire			Comment/Notes	
During the caesarean opera was it to insert the suction tub 0=Easy; 1 = Difficult; 2 = V not possible; 4 = unsure; 9 =	oe in the uterus? ery difficult; 3 =			
Did the suction tube help wit blood from the surgical site of the uterus? 0=No; 1 = A lit = not used; 4 = unsure; 9 = r	during closure ttle; 2 = A lot; 3			
After closure of the uterus, described tube seem to help with utering 0=No; 1 = A little; 2 = A lot; 3 unsure; 9 = no data	ne contraction?			
Please could you describe hoverall about the suction tub 0= negative; 1 = Positive; 2 = unsure; 9 = no data	e procedure?			
Thank you for assisting with	this questionnai	re		
Completed by (initials):		Date com	nleted	(dd/mmm/vy

References

- ¹ Pingray V, Widmer M, Ciapponi A, Hofmeyr GJ, Deneux C, Gülmezoglu M, Bloemenkamp K, Oladapo OT, Comandé D, Bardach A, Vázquez P, Cormick G, Althabe F. Effectiveness of uterine tamponade devices for refractory postpartum haemorrhage after vaginal birth: a systematic review. BJOG. 2021 Oct;128(11):1732-1743. doi: 10.1111/1471-0528.16819
- ² Kellie FJ, Wandabwa JN, Mousa HA, Weeks AD. Mechanical and surgical interventions for treating primary postpartum haemorrhage. Cochrane Database Syst Rev. 2020 Jul 1;7(7):CD013663. doi: 10.1002/14651858.CD013663.
- ³ Althabe F, Therrien MNS, Pingray V, Hermida J, Gülmezoglu AM, Armbruster D, Singh N, Guha M, Garg LF, Souza JP, Smith JM, Winikoff B, Thapa K, Hébert E, Liljestrand J, Downe S, Garcia Elorrio E, Arulkumaran S, Byaruhanga EK, Lissauer DM, Oguttu M, Dumont A, Escobar MF, Fuchtner C, Lumbiganon P, Burke TF, Miller S. Postpartum hemorrhage care bundles to improve adherence to guidelines: A WHO technical consultation. Int J Gynaecol Obstet. 2020 Mar;148(3):290-299. doi: 10.1002/ijgo.13028.

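### The CRF as shown has no code for failed insertion and no field for tube blockage or poor suction, so device deficiencies noted at the bedside have no stated route into the dataset

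*Protocol*

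**What the plan says.** Under Outcomes, the protocol states: "The primary outcome is the combined frequency of adverse device effects and device deficiencies up to discharge from hospital". As examples it gives "device deficiencies such as device expulsion / falling out of the uterus, failed maintenance of suction pressure and tube blockage". Among the secondary outcomes, 10f grades ease of insertion as "easy/moderately difficult/Difficult/failed" and 10k asks about blockage.

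The CRF grades insertion on three levels: "21. Ease of insertion? 1=easy, 2=mod.diff, 3=difficult". Item 22 records whether the device was stable and item 23 whether the tube leaked air. The next item printed is 25.

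Both clinical checklists offer failed and not done as insertion results (vaginal step 11, caesarean step 9). Step 26 of the caesarean checklist adds "Suction tube problems: Fell out; blocked; leaking; Poor suction", with a further option for none.

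The vaginal provider questionnaire asks about stability, air leak, blockage and ease of removal. The caesarean one asks about insertion, clearing of blood, uterine contraction and overall opinion.

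On data flow, the Quality assurance section makes the checklist part of the patient's clinical record and has completed CRFs checked against patient records. Data management has CRF data entered into a spreadsheet and analysed.

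**The concern.** A primary outcome made up of device faults can only be counted if the form behind the dataset has somewhere to put each fault. On the pages shown, blockage and poor suction have no such place, and neither does the lowest level of outcome 10f. The attending clinician notes these events on a checklist that stays in the hospital record, and no section says that its tube-problem item is transcribed. The primary rate and outcomes 10f and 10k could then rest on incomplete data, although the information was collected.

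**Working it through.** The point concerns form content and rests on no figure of the plan. The check sets each component against the forms as shown.

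| Component | Outcome | CRF | Caesarean checklist | Vaginal provider form | Caesarean provider form |
|---|---|---|---|---|---|
| Expulsion | Primary, 10g | Item 22 | Step 26 | Yes | No |
| Suction lost by air leak | Primary, 10h | Item 23 | Step 26 | Yes | No |
| Suction lost otherwise | Primary | None visible | Step 26 | No | No |
| Blockage | Primary, 10k | None visible | Step 26 | Yes | No |
| Failed insertion | 10f | No code in item 21 | Step 9 | Yes (not possible) | Yes (not possible) |

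The vaginal checklist also records failed insertion. Its step 27 is damaged in the text and shows only the option for none, so its list of tube problems cannot be read.

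**Is an air-leak item enough for lost suction?** The caesarean checklist lists leaking and poor suction as separate problems. By the protocol's own classification, CRF item 23 therefore covers only one of the two.

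**Does the check against patient records close the gap?** It verifies the fields that the CRF has. It cannot supply a field that is absent.

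**Do the adverse event forms close it?** They are for adverse events. A tube that blocks without harming the participant is a device deficiency but need not be an adverse event.

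**Item 24.** It is missing between items 23 and 25. A row may have been lost in conversion, or the form may be misnumbered (two items carry the number 53). The missing code in item 21 and the gap in the caesarean provider form do not depend on this.

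**Size.** The planned number of device users is 40 (Sample size), so one event missed changes the observed rate by 1/40 = 2.5 percentage points.

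Exact (Clopper-Pearson) upper limits for x events in 40 are quantiles of the Beta(x + 1, 40 − x) distribution, at 0.90 for a one-sided 90% limit and at 0.975 for a two-sided 95% interval:

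| Events in 40 | One-sided 90% upper limit | Two-sided 95% upper limit |
|---|---|---|
| 0 | 5.6% | 8.8% |
| 1 | 9.4% | 13.2% |
| 2 | 12.8% | 16.9% |

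The documents give no capture rate, so an overall bias cannot be calculated.

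**The case against.** The case against is substantial, and much of it stands.

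- **Failed insertion is not a named component of the primary outcome.** It is a level of secondary outcome 10f. It could enter the primary only through the general wording on deployment and installation problems, which requires an adverse event. This stands.
- **Some components are carried.** CRF item 22 covers expulsion and item 23 part of lost suction. The caesarean provider form can record that insertion was not possible. CRF item 19 may show that no device was inserted, but its codes are cut in the text. This stands and narrows the gap.
- **Other routes exist.** The CRF has a column for descriptions and an item for other complications, and adverse events have their own forms. These could catch some faults, but none prompts for a blocked tube or poor suction.

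A reader might infer more than the documents support:

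- **That a missing entry would count as no deficiency, biasing the rate downwards.** No section says this. Data analysis promises counts of missing values, and the CRF has a code for unknown.
- **That the loss would fall mainly at caesarean.** One CRF serves both modes, and the caesarean checklist is the one on which the full list can be read. The asymmetry lies in a provider questionnaire that asks for opinions, may be left unanswered and is not named as a source for the primary outcome.
- **That one missed event would move the result across 10%.** The protocol sets no pass or fail rule; 10% appears only in the sample size statement. The step from two events to one crosses 10% on a one-sided 90% limit, but the plan reports 95% confidence intervals. On the two-sided 95% limits, both values lie above 10%, and the crossing is between one event and none.

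A single ease-of-insertion scale on all forms would be tidier. The provider questionnaires are separate instruments, however, and the point does not need it.

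**Conclusion.** The mismatch between the forms and the outcomes holds. CRF item 21 cannot record a level that outcome 10f defines. The CRF as shown has no field for blockage, or for suction lost other than by air leak, although both belong to the primary outcome. The caesarean provider form lacks device questions that the vaginal form has, and the checklist's tube-problem item has no stated route into the dataset.

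This is a risk of incomplete capture, worth 2.5 percentage points per missed event in 40 device users. How many events would be missed, and at which mode of birth, cannot be determined from the protocol. The blockage part assumes that item 24 does not already hold it. The rest assumes that the CRF pages are otherwise complete and that the dataset is built from the CRF, as Data management describes. The point should be settled before recruitment because it touches the primary outcome and costs little.

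**What to change.** Before recruitment:

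1. Add codes for failed and not done to CRF item 21, to agree with outcome 10f and both checklists.
2. Copy the checklist's tube-problem item into the CRF for both modes of birth, with options for fell out, blocked, leaking, poor suction and none. If item 24 already records blockage, the blockage option is not needed.
3. Add the vaginal provider form's questions on stability, leak, blockage and removal to the caesarean provider form.

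The cost is a few extra form lines. The checklists already note failed insertion for both modes and, legibly at caesarean, the tube problems, so little or no new bedside recording is needed. The protocol already plans to pilot the CRFs before recruitment, and the revised forms can be tried then.
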